- Assessment of primary outcomes (drug use) will be conducted at baseline and monthly post-randomization (T1-T12). Secondary outcomes will be conducted at four time points: baseline, 4-, 8-, and 12-months post-randomization.

3.1 Design:

- Randomized “intent to treat” design.
- Informed assent will be obtained from adolescents (ages 12 to 17 inclusive) and consent from a parent or legally authorized guardian. Consent from the guardian will include the adult’s agreement to participate in research, consent for the adolescent to participate in the research study, and consent for any other minors under the age of assent. Additional adults and minors in the family will also be consented/assented prior to participation in any aspect of the study.
- Following consent, participants (adolescent, parents, and family members) will complete a baseline assessment (B1).
- Following the baseline assessment (B1), participants will be randomly assigned to BSFT or TAU.
- Treatment in both conditions will be provided in non-restrictive, community settings (e.g., clinic, home, and school). BSFT consists of 12 to 16 sessions (each approximately 1 to 1.5 hours long) over a 4-month period, plus up to 8 “booster” sessions. TAU will vary depending on the current activities at participating CTPs. For the purpose of this study, it is recommended that TAU in participating CTPs consist of at least 1 therapy session per week and may include participation in ancillary services (e.g., case management, AA, etc.) for a minimum of 3 to 4 months.
- Follow-up assessments of primary outcomes (drug use) will be conducted at monthly intervals following randomization (T1-T12).
- Follow-up assessments for secondary outcomes will be conducted at 4-, 8-, and 12-months following randomization.
- Measures of service utilization (including attendance in study intervention sessions) and adverse events will be conducted at 2-, 4-, 8-, and 12-months post-randomization.
- Alliance with therapist will be assessed 2- and 4-months post-randomization.
- AEs and SAEs will be reported whenever they are identified.

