estimate the random effects associated with each level of nesting. If any of these are statistically not significantly different from zero, we will drop these from the specification, prior to testing of the hypotheses. Note further, that as described below, the Hierarchical Linear Model (HLM) to be used to test our hypotheses is described with only a linear term in time. During our examination of the levels of nesting we will also examine the trajectories (again blind to condition) to ascertain any higher order polynomial trends in the data. For example, if a quadratic term in time is found to have significant variance over individuals, we will include the quadratic term in the HLM. The model as presented below does not show the nesting of 28-day periods within assessments and only shows the linear term of the growth model in an effort to keep the notational clutter to a minimum.

Analysis. Hypothesis 1 will be tested using hierarchical linear models (HLM) (Bryk & Raudenbush, 1992) to estimate the growth curve of drug use post-randomization. The trajectory of change in drug use will be compared between BSFT and TAU. HLM controls for the nesting of both repeated observations within the same adolescent over time and the nesting of adolescents within a CTP and further allows for a single test of the effect of the intervention across multiple times and sites (see planned post-hoc tests, below). HLM allows for the flexible inclusion of adolescents who may have missed assessments, and allows for non-linearity of the trajectory of change in the dependent measure. Finally, HLM allows us to consider treatment site as a random effect and to examine variability in treatment effects across sites. The treatment of site as a random effect is in keeping with the mission of the CTN to test the general applicability of proven treatments in real world settings. Thus, it is a goal of this protocol to show that BSFT will be efficacious in the population of community treatment providers, not just the community treatment providers in the sample (which a fixed effect specification would imply). This specification of the test actually compares the effectiveness of BSFT relative to the average effectiveness of TAU in the sites in the protocol. The analysis will include as a covariate referral from an institution for the treatment of drug.

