10.2.4 Test of Hypothesis

The primary test of hypothesis 1 is a test of the significance on the coefficients on the BSFT term alone from the intercept equation-- γ_{000} , and the term that includes BSFT interacted with a_{ijt} from the equation for the slope of the growth curve-- γ_{001} . If γ_{000} is significantly less than zero, then BSFT participants (on average across all the treatment sites) will have achieved lower drug use immediately post intervention than did the TAU participants. If γ_{001} is significantly less than zero, then BSFT participants (on average across all treatment sites) will have had a decrease in drug use relative to the TAU participants from immediately post-intervention to 12months post intervention. Conversely if γ_{000} and γ_{001} are significantly greater than zero, then BSFT participants will have, respectively, greater drug use immediately post-intervention and greater increase in drug use relative to TAU participants. To simplify the presentation and interpretation of results, planned contrasts will also test if there are differences between BSFT and TAU at each follow-up time point (T4 to T12).

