10.2.6 Planned Post Hoc Analysis

In most hypotheses, HLM has been used to minimize the number of statistical tests per hypothesis. In the case of a significant effect of BSFT in any of these hypotheses, planned post-hoc tests will look at the time path of this difference and document when the simple differences are statistically significant.

An additional sequence of analyses will be done to address variability in the effect of BSFT. This will be accomplished by adding explanatory variables associated with the sites in the equations at Level 3 for the intercept and slope. For example, because TAU services are not standardized, additional planned analyses will be conducted to examine the effectiveness of BSFT compared to various types of TAU services (e.g., individual therapy, group therapy, day treatment, recreational treatment). These analyses will include full exploration of the planned characterization of TAU services at each CTP. These analyses will also examine if there are differential attrition rates in different types of TAU services, and if BSFT is more effective than TAU when controlling for different engagement and retention rates across TAU services. As such, these analyses will help to address the possibility that TAU is just as effective as BSFT for those cases that remain in treatment. In all of these analyses, referral from an institution for the treatment of drug use will be entered as a covariate.

Companion analyses will examine whether patient characteristics, after controlling for TAU differences, are related to effectiveness of the BSFT intervention. These will be accomplished by adding explanatory variables in the equations for Level 2 for the intercept and slope. Variables to be considered include: age, gender, ethnicity/race, level of drug use, primary drug of abuse, family type, and baseline levels of internalizing/externalizing problems, family and peer functioning. This will answer the question of for whom the intervention worked.

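### Section 10.2.4 plans BSFT-versus-TAU contrasts at T4 to T12 unconditionally, while 10.2.6 makes time-point tests follow a significant BSFT effect; the two rules part when the overall result is null

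*Protocol*

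**What the plan says.** All references are to the protocol.

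- **Section 10.2 (Analysis)** gives as a merit of the hierarchical model that it "allows for a single test of the effect of the intervention across multiple times and sites (see planned post-hoc tests, below"). Time points are thus left to the post-hoc section.
- **Section 10.2.4** names the primary test: "The primary test of hypothesis 1 is a test of the significance on the coefficients on the BSFT term alone from the intercept equation", together with the BSFT-by-time term from the slope equation. Its last sentence adds the monthly comparisons, as an aid to presenting and interpreting the results: "planned contrasts will also test if there are differences between BSFT and TAU at each follow-up time point (T4 to T12"). It states no condition.
- **Section 10.2.6** says that "HLM has been used to minimize the number of statistical tests per hypothesis", and continues: "In the case of a significant effect of BSFT in any of these hypotheses, planned post-hoc tests will look at the time path" of the difference and "document when the simple differences are statistically significant".
- **Section 3.1** fixes the schedule: "Follow-up assessments of primary outcomes (drug use) will be conducted at monthly intervals following randomization (T1-T12"). T4 to T12 is therefore nine time points.

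**The concern.** Sections 10.2.4 and 10.2.6 describe the same comparisons, BSFT against TAU by time point on the primary outcome, under different rules. If the overall effect is significant, both lead to monthly tests and nothing turns on the difference. If it is not, 10.2.4 read alone still produces nine p-values, and 10.2.6 gives no ground for any.

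A null or borderline result is where a pre-stated rule matters most. An analyst could then report a significant month as a planned contrast and cite 10.2.4, or report none and cite 10.2.6, and claim compliance either way. This is not a gap that a statistical analysis plan would ordinarily fill, because the protocol has already written both rules down.

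**Working it through.** **1. The two rules side by side.**

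| Overall BSFT effect | 10.2.4 | 10.2.6 |
|---|---|---|
| significant | nine contrasts tested | time-point tests follow |
| not significant | nine contrasts tested | none provided for |

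They differ in the second row only.

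**2. Level of test.** The protocol gives no error rate for these contrasts. Section 13.0 refers to an overall type 1 error of 0.05. The power figures in 10.4.1 agree with a test at that level. With λ = Jδ²/(σ² + 4/n), J = 8, δ = .45, n = 57 and σ² = .10, λ = 8 × .2025 / (.10 + 4/57) = 1.62 / .1702 = 9.52. Noncentral F(1, 7) then gives 75.4% against the stated 75%. At σ² = .15 the result is 64.5% against 64%. At σ² = .05, assumed because the small value is not legible, it is 88.1% against 87%. I use .05 two-sided per contrast; 10.2.4 does not state a level.

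**3. What the contrasts are.** I use the labels of 10.2.3, where γ100 and γ101 are the BSFT effects on intercept and slope. Time is centred on T4, so in the linear model the arm difference at month t is

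D(t) = γ100 + γ101 (t − 4), for t = 4, ..., 12.

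At t = 4 this is γ100, the intercept effect that is already in the primary test. The other eight are linear combinations of the two primary coefficients. Hence no z² from a contrast can exceed the joint 2-df chi-square. Whatever the correlation, the chance of any significant month is at most P(χ² on 2 df > 1.96²) = exp(−1.92) = 14.7%.

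**4. Null simulation.** Inputs: model fitted to T1-T12 (10.2.1 uses all times after baseline); 240 per arm (480/2; arm size cancels from z under the null); compound-symmetric correlation ρ of .1, .3 and .5. Section 10.4.1 assumes .1 and calls .2 to .4 not uncommon. Coefficients are drawn from a normal distribution with mean 0 and covariance (2/240)(X′V⁻¹X)⁻¹. Each D(t) is divided by its standard error and compared with 1.96. The joint test is a chi-square on all BSFT terms in the model: 2 df linear, 3 df quadratic. Site random effects are left out; 400,000 draws.

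| ρ | Linear: any month | Linear: any month, joint test not significant | Quadratic: any month | Quadratic: any month, joint test not significant |
|---|---|---|---|---|
| .1 | 10.8% | 6.3% | 14.3% | 10.1% |
| .3 | 9.0% | 5.2% | 11.6% | 8.1% |
| .5 | 7.9% | 4.4% | 9.9% | 6.8% |

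**5. Sensitivity.** With random slopes, or with the linear model fitted to T4-T12 only, the linear figures move to about 9-12.5% for any month, and 5.2-7.5% for a month without a significant joint test.

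**6. Effect of a gate.** If months are tested only after a significant joint test at .05, the chance under the global null of any reported significant month cannot exceed 5%. Subtracting the columns above gives 10.8 − 6.3 = 4.5% down to 7.9 − 4.4 = 3.5% (linear), and 14.3 − 10.1 = 4.2% down to 9.9 − 6.8 = 3.1% (quadratic).

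**The case against.** The best defence is that there is no real conflict. Section 10.2.4 names two coefficients as the primary test and gives the contrasts a modest purpose, presentation and interpretation. Section 10.2.6 can be read as the general rule for when they are used. It does not contain the word only, and 10.2.4 does not say that the contrasts run whatever the growth model shows. Multiplicity for supportive contrasts is also commonly left to a statistical analysis plan.

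Much of this stands, and it rules out several stronger readings:

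- A reader might infer that a single month can decide Hypothesis 1. Nothing in the protocol lets it; sections 10.2 and 10.2.4 point the other way.
- A reader might treat the contrasts as nine independent tests, giving 1 − .95⁹ = 37.0%, or as separate monthly analyses, giving 27-36% at correlations of .5 to .1. The plan describes contrasts within a growth model, and in the linear case step 3 caps the rate at 14.7%.
- A reader might count the nine as wholly additional to the primary test. The T4 contrast is one of its coefficients and, in the linear model, the rest are built from the two. A month is significant while neither coefficient is in only 1.6-5.8% of null trials (linear).
- A reader might say that the protocol prescribes unadjusted tests. It is silent on adjustment, and silence alone is no fault here.

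What does not stand is that the two sections already agree. The conditional opening of 10.2.6 has no function if the same tests run regardless, and 10.2.4 neither repeats the condition nor refers to it.

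**Conclusion.** The inconsistency holds, and it concerns supportive analyses. Followed as written, 10.2.4 allows month-specific significance claims after a null overall result; 10.2.6, and the single-test intention of 10.2, do not provide for them. The excess is moderate: under the null, roughly 4-6% of trials (linear) or 7-10% (quadratic) would show a significant month without a significant joint test.

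These rates assume .05 two-sided per contrast, large-sample normal tests, compound symmetry at .1 to .5 and no site random effects. The protocol gives no variance components, so the range matters more than any one figure. The primary test and the power figures are unaffected.

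**What to change.** Replace the last sentence of 10.2.4 with:

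> Model-based differences between BSFT and TAU at T4 to T12 will be presented as estimates with 95% confidence intervals; they will be tested for significance only if the joint test of the BSFT intercept and BSFT-by-time terms is significant at .05, as in 10.2.6.

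If a quadratic term is kept, its interaction with BSFT belongs among the BSFT-by-time terms. Naming the joint test is needed because 10.2.4 lists two coefficients without saying how they combine, so a gate on the overall effect would otherwise be undefined.

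No Holm step is needed to hold the rate at or below 5% under the global null. Adding one would judge the T4 difference under two rules, once as a primary coefficient and once as an adjusted contrast.

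The cost is one sentence, with no change to data collection, sample size or model. What is given up is any month-specific significance claim when the overall test fails; estimates and intervals would still be shown.

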10.2.5 Advantages of Statistical Model

There are several advantages to this approach. First, in the test here, a_{ijt} is the time (in 28-day “months”) since T4 (approximately 4 months post-randomization). Thus, assessments are not required to be at the same or at equally spaced intervals across individuals. Second, these equations, as presented, assume a linear growth curve, if there is evidence of quadratic trends in the outcome, these will also be modeled, but they are omitted here for ease of exposition.

10.2.6 Planned Post Hoc Analysis

In most hypotheses, HLM has been used to minimize the number of statistical tests per hypothesis. In the case of a significant effect of BSFT in any of these hypotheses, planned post-hoc tests will look at the time path of this difference and document when the simple differences are statistically significant.

An additional sequence of analyses will be done to address variability in the effect of BSFT. This will be accomplished by adding explanatory variables associated with the sites in the equations at Level 3 for the intercept and slope. For example, because TAU services are not standardized, additional planned analyses will be conducted to examine the effectiveness of BSFT compared to various types of TAU services (e.g., individual therapy, group therapy, day treatment, recreational treatment). These analyses will include full exploration of the planned characterization of TAU services at each CTP. These analyses will also examine if there are differential attrition rates in different types of TAU services, and if BSFT is more effective than TAU when controlling for different engagement and retention rates across TAU services. As such, these analyses will help to address the possibility that TAU is just as effective as BSFT for those cases that remain in treatment. In all of these analyses, referral from an institution for the treatment of drug use will be entered as a covariate.

Companion analyses will examine whether patient characteristics, after controlling for TAU differences, are related to effectiveness of the BSFT intervention. These will be accomplished by adding explanatory variables in the equations for Level 2 for the intercept and slope. Variables to be considered include: age, gender, ethnicity/race, level of drug use, primary drug of abuse, family type, and baseline levels of internalizing/externalizing problems, family and peer functioning. This will answer the question of for whom the intervention worked.

Therapist differences might also be an important source of variability in outcomes. In fact, the effect of participants being nested within therapist might be modeled similarly to the site effect in the planned primary analysis. In planned post-hoc analyses we will explore the effect of adding therapist as a fourth nesting factor (between participants and sites). We will also see if there are particular therapist characteristics (e.g., training, experience) or therapeutic processes (e.g., alliance) that explain this source of variance.

Further analyses will establish the effect-sizes within each of the sites and examine whether patient characteristics differed by site, and thus might explain any observed variability in effect size across sites. As stated above, the primary test of the effectiveness of BSFT is an average of the effectiveness across sites. Whereas it is not expected, it is possible that a site or sites might have TAU results that are more effective than BSFT (a negative effect) but still on average across sites show BSFT to be more effective. This planned post-hoc analysis will document that this is or is not the case.

Analyses of alternative formulations of the drug use outcome variable will be explored to provide evidence for planning of future drug abuse trials with adolescents. Specifically we will look at various ways of weighing drug use days by the number of drugs used in the day. This variable may be more sensitive to poly-drug use, however standard psychometrics including reliability and validity are not presently available.

Finally, whereas the primary outcome in this proposal is related to the functioning of the participating adolescent, family therapy modalities also are likely to affect all family members. Thus a post-hoc analysis will be done examining the changes in parent alcohol and drug use using the ASI done on the parent.

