1.3.2 Engagement and Retention of Drug Abusers

Engaging and retaining drug abusers is one of the most important, albeit difficult aspects of drug abuse treatment. This problem is further exacerbated when the drug abuser is an adolescent, though it is just as much a problem with adults (Diguseppe, Linscott, & Jilton, 1996). BSFT has developed, evaluated, and integrated specific strategies for engaging and retaining drug abusing adolescents and their family members in treatment. In separate studies, the effectiveness of specialized BSFT engagement strategies in engaging and retaining drug abusing adolescents and their families in treatment have been demonstrated.

[name], Perez-Vidal, et al. (1988). 108 Hispanic drug-abusing adolescents (ages 12-21) and their families were randomly assigned to one of two conditions: (a) BSFT with specialized engagement strategies; and (b) BSFT with engagement as usual. With successful engagement defined as completion of an intake assessment, 92.9% of families in the BSFT+Specialized Engagement condition were successfully engaged, as compared to 42.3% of the families in the BSFT+Engagement as Usual; $\chi^2 (1, N = 108) = 29.64, p < .0001$. Continuing to use the same specialized engagement strategies to retain cases in treatment in the experimental conditions, 77% of families in the BSFT+Specialized Engagement condition successfully completed a full dose of therapy (approximately 8 sessions), compared to 25% of families in the BSFT+Engagement as Usual condition; $\chi^2 (1, N = 108) = 26.93, p < .0001$.

Santisteban et al., (1996). This study replicated and extended the findings of the initial engagement study. This study included more stringent criteria for successful engagement (i.e., intake assessment plus first therapy session), a second control group (group treatment with engagement as usual), and a more culturally diverse sample (i.e., a larger percentage of non-Cuban Hispanics). 193 Hispanic drug-abusing adolescents and their families were randomly assigned to the three conditions. Results indicated that the BSFT+Specialized Engagement condition was again associated with higher rates of successful engagement (81%) than were the two control groups (60%), $\chi^2 (1, N = 193) = 7.50, p < .006$.

1.3.3 Externalizing Behaviors (as measured by the Revised Behavior Problem Checklist and reported by a parent/guardian [Quay and Petersen, 1987; Rio, Quay, Santisteban, & [name], 1989]).

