10.3 Secondary Outcomes and Hypothesis

There are five categories of secondary outcomes: a) engaging adolescents and family members in treatment, b) decreasing externalizing problem behaviors, c) decreasing adolescent sexually risky behaviors, d) increasing adolescent prosocial activities (e.g., school, employment), and e) improving family functioning (e.g., parenting, parent-adolescent relations). Please note that these secondary outcomes are only measured at B1, T4, T8 and T12.

Hypothesis 2a: BSFT will be significantly more effective in engaging participants in treatment than will TAU.

Outcome Variable. Engagement is defined as attendance by adolescent and/or family members at a minimum of two therapy (treatment) sessions. For BSFT, these will be BSFT sessions, for TAU, these will be defined in a manner that is consistent with the services provided (e.g., individual, group or non-manualized family therapy, day treatment).

Analysis. Hypothesis 2 will be analyzed as in Hypothesis 1 using hierarchical linear models (HLM) (Bryk & Raudenbush, 1992). However, in this analysis a logistic link function will be used due to the 0-1 nature of the outcome. Note that because this outcome is not a time-related value, that trajectories are not involved, however all other levels of nesting described in the primary analysis are still in effect and therefore HLM is still the method of analysis. In planned post-hoc analysis

[name]

engagement of adolescents and family members (i.e., attendance in therapy sessions), specifically will be examined.

Hypothesis 2b. BSFT will be significantly more effective than TAU in decreasing externalizing problem behaviors.

Outcome Variable. For Hypothesis 2b, a composite of the following scales will be used: ‘Total Delinquency’ from the National Youth Survey; ‘Oppositional Defiant Disorder’ and ‘Conduct Problems’ from the Diagnostic Interview Schedule for Children-Predictive Scales, and the ‘Externalizing Scale’ from the Youth Self-Report. A confirmatory factor analysis will be conducted to determine that these scales measure a single construct. Reliability of this construct when loadings are constrained to be 1 will be calculated and if sufficient, equally weighted composite scores will be constructed. Otherwise, factor scores will be created using the estimated loadings and the resulting composite will be used to examine hypothesis 2b.

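### The planned retention-controlled comparison cannot show whether TAU is as effective as BSFT among youths who stay in treatment, and its bias is of unknown direction

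*Protocol*

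**What the plan says.** Protocol section 10.2.6 describes a set of post hoc analyses meant to explain why the BSFT effect varies. They are to be done by "adding explanatory variables associated with the sites in the equations at Level 3 for the intercept and slope". Within that set, the plan will examine differential attrition by type of TAU service and also "if BSFT is more effective than TAU when controlling for different engagement and retention rates across TAU services". The stated purpose is that "these analyses will help to address the possibility that TAU is just as effective as BSFT for those cases that remain in treatment". No caution or identifying assumption is attached to that reading.

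Elsewhere the protocol treats engagement as something BSFT should change:

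- Section 10.3, Hypothesis 2a: "BSFT will be significantly more effective in engaging participants in treatment than will TAU".
- Same section, definition: "Engagement is defined as attendance by adolescent and/or family members at a minimum of two therapy (treatment) sessions". These sessions take place after randomization.
- Section 1.3.2 says BSFT has built in strategies both to engage and to retain adolescents and their families.
- Section 5.2.1 lists engaging the family as one of BSFT's three classes of intervention.

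**The concern.** Randomization makes the two arms comparable as assigned. It does not make the youths who stay under BSFT comparable with those who stay under TAU once the arm itself affects who stays. A difference between these two groups mixes the treatment effect with the difference in who they are, and an absence of difference is equally uninterpretable. Adjusting for retention also takes out whatever BSFT achieves by keeping families in treatment, which is part of its effect.

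Whether BSFT adds anything once a youth is retained is a question that a program considering adoption could reasonably ask. The protocol says in advance that this analysis bears on it, so a result in either direction could be reported as an answer it cannot give.

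**Working it through.** **Plan's own figures.** The protocol gives no figure for this analysis. The nearest is in section 10.4.3: with 45 per condition and 40% engaged in TAU, 69% in BSFT gives 80% power. A two-proportion calculation at two-sided 5% (assumed) returns 79.9%, so that figure reproduces. It confirms that the plan contemplates an arm difference in engagement. The low end of the engagement gap quoted in section 10.4, 21 points, equals 81% − 60% from section 1.3.2.

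**Illustration 1: one shared propensity to stay (individual-level, assumed).**

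- Inputs: retention p = 0.81 (BSFT) and 0.60 (comparator), borrowed from the engagement rates in section 1.3.2; no treatment effect; correlation ρ of 0.2 to 0.3 between propensity to stay and a better outcome. The value of ρ is not in the documents.
- Formula: mean propensity among those retained = φ(z)/p, where z cuts off the upper fraction p of a standard normal.
- BSFT: 0.2714/0.81 = 0.335. Comparator: 0.3863/0.60 = 0.644. Difference: 0.309.
- Spurious difference: 0.2 × 0.309 = 0.06 SD; 0.3 × 0.309 = 0.09 SD, against BSFT.
- Relative to the design effect of .45: 0.062/0.45 = 14% to 0.093/0.45 = 21%.

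**Illustration 2: is the sign fixed?** The retention rates are the same and the true effect is zero. The assumed correlation of severity with outcome is 0.5, and the correlation of severity with leaving is set separately in each arm (1,000,000 simulated participants per row). Positive values go against BSFT, in SD units.

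| Severity–leaving, BSFT | Severity–leaving, TAU | All randomized | Retained only | Retention as covariate |
|---|---|---|---|---|
| 0.5 | 0.5 | 0.00 | +0.08 | +0.09 |
| 0 | 0.5 | 0.00 | +0.16 | +0.05 |
| 0.5 | 0 | 0.00 | −0.08 | +0.04 |
| 0.5 | −0.2 | 0.00 | −0.15 | +0.02 |
| −0.5 | −0.5 | 0.00 | −0.07 | −0.09 |
| 0 | 0 | 0.00 | 0.00 | 0.00 |

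The comparison of everyone randomized stays at zero. The conditioned contrasts move either way, and in two rows the two forms of conditioning disagree in sign.

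**Illustration 3: effect through retention only.** Assume staying lowers drug use by 0.4 SD and is unrelated to severity. The total effect is −0.4 × (0.81 − 0.60) = −0.08 SD. After adjustment for retention it is 0.00, so the whole effect disappears from view.

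**If the rates enter at Level 3.** Illustrations 1 to 3 do not carry over to this reading. A rate attached to a site or service is the same for every youth there. It can describe how the BSFT effect varies across sites, but that is a non-randomized comparison over about 8 points (section 10.4). It does not identify which youths stayed, so it cannot speak to individual retained cases.

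**The case against.** The strongest reply is that the protocol does not specify a retained-only subset or an individual retention covariate. It speaks of rates across TAU services, entered at Level 3, to explore uneven TAU. The analysis is labelled post hoc, the wording is hedged, and detail could sit in an analysis plan not shown here. The primary analysis includes everyone randomized (section 4.7.2), and youths who leave treatment continue to be assessed (sections 4.7.1 and 10.1.1). The illustrative bias is also small beside sampling error. With an assumed 240 per arm, 0.81 × 240 ≈ 194 and 0.60 × 240 = 144 would be retained, and √(1/194 + 1/144) ≈ 0.11 SD.

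Most of this stands and limits the weight of the point. It does not rescue the stated inference. The protocol itself says the analyses bear on cases that remain in treatment, and neither the individual-level nor the site-level version can support that.

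A reader might go further in three ways that the documents do not support:

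- **That the comparison is biased against BSFT.** This follows only if BSFT holds harder cases that TAU loses. The protocol does not say who stays in either arm, and the sign reverses under other patterns.
- **That the completion gap in section 1.3.2 shows a much larger bias.** There, "77% of families in the BSFT+Specialized Engagement condition successfully completed a full dose of therapy (approximately 8 sessions), compared to 25% of families" given engagement as usual, but both arms of that study received BSFT. It is not a BSFT–TAU gap.
- **That Hypothesis 2a predicts better retention.** It concerns attendance at two or more sessions. A retention difference from TAU is a reasonable inference, not a stated figure.

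**Conclusion.** The point holds in limited form. The planned analysis conditions on events after randomization that the protocol expects, or may reasonably be taken to expect, BSFT to alter. The inference about youths who remain in treatment therefore does not follow. The bias has no known direction: against BSFT if it keeps harder cases that TAU loses, in its favour if severe cases are the ones that stay, and nil if staying is unrelated to prognosis.

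The figure of 0.06 to 0.09 SD is an illustration. It rests on an individual-level model, a single shared propensity to stay, an assumed correlation of 0.2 to 0.3, and engagement rates standing in for retention. Those rates come from a study that defined engagement as intake plus a first session and pooled two control groups, so they only approximate this trial.

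The intent-to-treat primary analysis is unaffected. The matter should be corrected because it changes what the trial may claim, but it does not threaten the main result.

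**What to change.** In section 10.2.6, delete the sentence claiming that these analyses address whether TAU is just as effective among cases that remain in treatment. Label any retention-adjusted or retained-only contrast descriptive and non-causal. Keep the planned reporting of differential attrition by type of TAU service. This costs only wording.

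If the sponsor wants the question answered, define the estimand as the effect in participants who would remain in treatment under either arm. Predict retention from baseline variables already collected (such as comorbidity, drug diagnosis, family functioning and referral source), state the assumptions, and report a sensitivity range. This is optional and one of several possible methods. It needs modest extra analysis on existing data, and its price is wider intervals and assumptions that cannot be tested.
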